## I. Objectives

The goal of this study is to assess if docosahexaenoic acid (DHA) and eicosapentaenoic acid (EPA) accumulate in blood lipids to the same extent when consumed as a fortified beverage as opposed to a traditional capsule as well as assess compliance to daily consumption, tolerance and acceptability of a fortified soymilk beverage.

It is hypothesized that DHA and EPA levels will be equivalent in erythrocytes after 4 weeks of fortified soymilk consumption as compared to commercial capsules.

We propose the following objectives:

- A. Evaluate the effect of EPA and DHA matrix (beverage or capsule) on accumulation of EPA and DHA in lipid pools over 4 weeks of daily consumption.
  1. EPA and DHA levels will be measured in erythrocytes, peripheral blood mononuclear cells (PBMC), platelets, and plasma over time.
- B. Assess suitability of soymilk as a delivery vehicle for EPA and DHA.
  1. Compliance will be measured using daily intake logs and the return of empty and full bottles of soymilk or remaining capsules
  2. Tolerability will be monitored using a daily symptom journal.
  3. Sensory acceptability will be monitored initially and after 4 weeks of consumption to validate long term use of the fortified soymilk.

## II. Background and Rationale

Research shows that fish oil and its component fatty acids EPA and DHA provide health benefits such as reducing the risk of cardiac death and lowering inflammation. Yet a large portion of the population is not consuming the recommended amount of fish due to high cost, dietary restrictions such as vegetarianism/veganism, concerns about high levels of mercury, general dislike, and other factors. Additionally, to meet the recommendations fish and fish oil production present sustainability challenges. A potential alternative is to utilize EPA and DHA from algae. Algae oil has performed equally to fish oil in several clinical studies and has been demonstrated as safe for consumption. These sustainable oils can be added to foods increasing the potential for fatty acids to counteract chronic disease and increasing access to general consumers.

Emulsification of omega-3 fatty acids and incorporation into food products have been shown in multiple studies to enhance short-term bioavailability of the oil. This pre-emulsification before digestion improves the rate and extent of incorporation into lipid pools. Some longer term studies of 4 weeks showed no difference or bioequivalence between algae or fish oil capsules and various fortified foods or microencapsulated oils. However, soymilk has not been assessed as a vehicle for EPA and DHA. Therefore, the bioavailability or bioequivalence to capsules needs to be measured. This study will offer valuable data showing that algae oil consumed in a soymilk matrix has the ability to alter lipid pools in the long term. This study will also provide preliminary data including compliance, sensory acceptability, and tolerability, validating the use of an algae oil fortified soymilk in future clinical studies.

Previously, our lab has developed, and optimized EPA and DHA fortified non-dairy plant milk beverages utilizing algae oil emulsions (food grade). Soymilk was chosen as the optimal vehicle due to its ability to mask some of the algae oil flavor, while maintaining stability of the fatty

acids. Up to 0.4% algae oil can be added to soymilk with limited changes to overall liking. Consumers did not prefer the control samples over 0.4% algae oil samples at statistically significant levels, meaning that they did not reject those samples. These samples were unflavored and addition of flavoring such as chocolate or vanilla is expected to increase sensory acceptability even more and mask algae oil flavor.

0.4% algae oil in 12 oz. of soymilk equates to approximately 700 mg of combined EPA and DHA (453 mg DHA and 249 mg EPA). In the 2020-2025 Dietary Guidelines for Americans, it was recommended to consume 8-12 oz of seafood per week, providing an average of 250-375 mg of the polyunsaturated fatty acids eicosapentaenoic acid (EPA) and docosahexaenoic acid (DHA). The dietary guidelines cite the reduction in risk of cardiac deaths and beneficial effects for women who are pregnant or breastfeeding as the primary reasons for the seafood recommendation. Based on these recommendations, 700 mg of EPA and DHA should be more than enough per serving. However, many studies looking at the health benefits of EPA and DHA from fish or algae use servings of around 1 gram or higher. Therefore, multiple servings could be given depending on the goals of the clinical trial.

This study will compare the algae oil fortified soymilk to a commercial algae oil capsule containing the same base oil with the goal of demonstrating equivalent or greater accumulation of EPA and DHA in blood lipid pools.

### III. Procedures

#### A. Research Design

This study will compare blood EPA and DHA concentrations over time after daily consumption of algae oil capsules or algae oil fortified soymilk. The proposed study is a randomized parallel arm trial involving 24 healthy participants. The study will be open label, since participants will know if they are consuming the study agent or pill. The intervention will include a 2-week placebo run-in phase and a 4-week intervention (Figure 1) with 4 total clinic visits to the OSU Clinical Research Center (CRC).

[figure not shown]

Figure 1: Study Design

## B. Sample

This study will include healthy participants aged 18-60 years of age with a body mass index (BMI) between 18 and 30 kg/m^2.

Exclusion criteria will include:

- Being pregnant or nursing
- Having anemia or a condition that influences the ability to donate blood safely
- Allergies to the beverage or pill ingredients
- Diabetes
- High triglycerides or cholesterol
- Coagulation disorder
- Anticoagulation therapy or any drug that affects blood clotting.
  - The NIH states that omega-3 supplements may interact with drugs that affect blood clotting (<https://www.nccih.nih.gov/health/omega3-supplements-in-depth>).
- Taking prescribed dietary omega-3 fatty acid medications including fish oil or algae oil within the last 3 months
- Taking non-prescribed dietary omega-3 fatty acid supplements within the last 3 months and not willing to discontinue taking them for the study period
- Taking lipid lowering medications such as statins
- Sensory impairments which affect ability to taste, smell, or see food products

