### *Informed Consent*

Persons who are interested and eligible will be scheduled for a Day -15 visit with a study coordinator at the CRC. On the first visit, participants will begin the informed consent process and all study procedures will be explained. If they agree to participate, subjects will be given a copy of the informed consent form for their records.

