### **C. Measurement and Instrumentation**

#### **1. Biological Measures**

The EPA and DHA concentration in multiple blood fractions will be measured including erythrocytes, peripheral blood mononuclear cells (PBMC), platelets, and plasma.

Erythrocyte fatty acids concentration correlates better with intake and reflect longer term intake as compared to plasma . Therefore, the primary objective is to determine if erythrocyte DHA and EPA levels differ after consuming algae oil fortified soymilk versus commercial algae oil capsules daily for four weeks.

A total of 24 mL of blood will be collected at each time point into two Vacutainer EDTA tubes (6 mL each) and 2 CPT tubes (8 mL each).

Blood collected into EDTA tubes will be inverted immediately following collection and then stored on ice until centrifugation (within 1 hour of collection). EDTA tubes will be centrifuged at 1932 x g for 10 minutes at 4°C. The plasma will be extracted and aliquoted into 2 mL tubes. Tubes will be stored on ice after aliquoting. The buffy coat layer will be removed and discarded, and the red blood cells will be extracted. The plasma and RBC aliquots will be stored at -80°C until analysis.

Blood collected in the CPT tubes will be prepared according to the manufacturer's instructions. The tubes will be stored upright and centrifuged within 2 hours of collection. The tubes will be inverted before centrifuging at 1800 x g for 30 minutes at room temperature. A portion of the plasma will be removed from the top of the tube and the cells will be resuspended in PBS buffer to a volume of 15 mL. The tube will be inverted to mix and centrifuged again at 300 x g for 15 minutes. The cells will be washed again with PBS. The remaining pellet will be mixed with 1 mL of PBS and then transferred to 2 mL tubes. After centrifuging again at 300 x g for 5 minutes the supernatant will be aspirated off and the cell pellet will be stored at -80°C until analysis.

Fasting blood samples at each time point will be collected into two Vacutainer tube containing EDTA and immediately stored on ice until centrifugation at 1932 x g for 10 min at 4C. Blood will also be collected in one CPT tube to be used for PBMC samples.

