### **Run-in Phase**

The study will include a 2-week placebo run-in phase where subjects will consume one serving of the control beverage per day with no algae oil. During the run-in the participants will complete a daily intake log, monitoring if and when they consumed the control beverage, as well as complete a log of symptoms, and sensory evaluation on the beverage. These tasks will help familiarize them to the procedures that will be performed during the rest of the study.

Additionally, the two weeks will serve as a washout where they will be instructed to avoid a list of foods and supplements containing EPA and DHA. A food frequency questionnaire will also be used to assess usual intake of fish, shellfish, and plant-based milk beverages and healthy eating index.

Participants will be asked if they would like to receive email reminders detailing daily tasks. If so, study coordinators will send emails reminding the subjects of each daily task including drinking the beverage or taking the pills, filling out the daily dairy and applicable DHQIII or sensory evaluation tasks. Additionally, each participant will be reminded of clinic visits and instructions to come having fasted for 12 hours.

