### **Study Phase**

After the run-in, the participants will then be randomized to the beverage or pill group. During the study phase, there will be three clinic visits to the Cancer Research Center. The visits will occur on day 0, 14, and 29. At each visit, blood will be drawn.

Additionally on days 1 and 28, they will perform a sensory evaluation on the beverage using provided forms. The second sensory evaluation will be used to determine if long-term consumption of the beverage impacted its perception.

Over the course of the 28 days, participants will complete daily intake and symptom logs to ensure compliance to the low marine omega-3 diet and study intervention as well as monitor adverse effects.

To ensure compliance during the study, participants will be asked to return empty beverage or pill containers and any that were not consumed. One to three extra beverages or pills will be given to estimate how many were consumed.

Participants will again be asked if they would like to receive email reminders detailing daily tasks.

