### **Internal and External Validity**

Subjects will be stratified by gender and randomized to the study arms to enhance study internal validity. Age, BMI, and initial EPA and DHA levels will be measured in all participants to ensure even distribution across study arms. If differences in these variables are found, they will be used as covariates in data modeling.

Efforts will be made to ensure a diverse sample of study participants by recruiting from various areas around campus and not just recruiting students. Women will represent 50% of the study participants. No participant will be excluded on the basis of race or ethnicity.

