### **Data Analysis**

All data analysis will be performed using SAS statistical software.

The impact of the algae oil form on the primary outcome of change in erythrocyte EPA and DHA concentration will be evaluated using analysis of variance (ANOVA). Covariates including BMI, height, weight, sex, age, ethnicity, and pre-trial and baseline levels of EPA and DHA will be evaluated using a forward selection procedure.

The influence of product type on secondary outcomes including EPA and DHA concentrations in other blood lipid pools will also be evaluated using ANOVA.

Compliance will be measured using the daily intake log and number of empty bottles, pills received at each clinic visit. The number of days that the beverage is consumed and any noncompliance with the marine omega-3 restricted diet divided by the number of total days will be used to report compliance.

Exploratory analyses including influence of algae oil vehicle on various blood lipids, hormones, and metabolites and the influence of diet on various variables may also be performed.

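### Two different data-driven rules decide whether the primary analysis adjusts for baseline EPA/DHA; one fixed model should replace both

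*Protocol*

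**What the plan says.** The primary outcome (Protocol, Data Analysis) is the change in erythrocyte EPA and DHA, compared by ANOVA. Two sections say how baseline values enter.

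- **Internal and External Validity.** Age, BMI and initial EPA/DHA are compared between arms, and then: "If differences in these variables are found, they will be used as covariates in data modeling". No criterion for a difference is given. It is also not said whether the initial level is the sample before the run-in or the day-0 sample. The same section states: "Subjects will be stratified by gender and randomized to the study arms".
- **Data Analysis.** BMI, height, weight, sex, age and ethnicity are listed as candidates, and with them "pre-trial and baseline levels of EPA and DHA will be evaluated using a forward selection procedure". No entry threshold is given, nor whether treatment is in the model during selection.

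The background to baseline levels lies elsewhere. B. Sample excludes people "Taking non-prescribed dietary omega-3 fatty acid supplements within the last 3 months and not willing to discontinue taking them for the study period", so a recent user who agrees to stop is eligible. Such a person is "scheduled for a Day -15 visit with a study coordinator at the CRC", and the run-in follows: "the two weeks will serve as a washout where they will be instructed to avoid a list of foods and supplements". Allocation comes later: "After the run-in, the participants will then be randomized to the beverage or pill group". Under 1. Biological Measures, erythrocytes are preferred because "Erythrocyte fatty acids concentration correlates better with intake and reflect longer term intake as compared to plasma".

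**The concern.** For the same variable, one rule looks at imbalance between arms and the other at association with the outcome. They can give opposite answers in the same data set, and nothing says which governs. The analyst would therefore settle the primary model after seeing the data.

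Forward selection in a trial this small also does harm on either reading. If treatment stays in the model, covariates that fit noise shrink the residual variance by more than the lost degrees of freedom account for. Standard errors are then too small. If covariates are chosen first, one that happens to be correlated with treatment can absorb part of the treatment effect. At stake are the error rate and interval width of the primary comparison. These matter the more because Objectives hypothesises equivalence, and an interval that is too narrow makes equivalence too easy to claim.

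**Working it through.** **1. The plan's own figure.** Sample size justification gives a difference of 20, SD 15, alpha 0.05 and power 0.80. A two-group ANOVA equals a two-sided t-test with 2n − 2 degrees of freedom and noncentrality 20 / (15 × √(2/n)). Power is 0.757 at n = 9, 0.805 at n = 10 and 0.877 at n = 12. Ten per group is reproduced. The 24 recruited equals 20 × 1.2.

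**2. Number of candidates.** Six characteristics plus the pre-trial and baseline levels make 8 candidates, or 6 + 2 × 2 = 10 if EPA and DHA count separately.

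**3. The imbalance rule.** The protocol gives no threshold. If a difference means p < 0.05, randomisation makes baseline enter in about 4–5% of simulated trials, however well it predicts change. Type I error is 0.035–0.05. With an assumed baseline–change correlation of size 0.5, power is 0.815, against 0.805 unadjusted and 0.90 with baseline always included.

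**4. Forward selection, 10 per arm.** The SD of change is 15, as in the plan. Entry p, correlations and carry-over are assumptions. Three set-ups were simulated: (A) ten independent candidates; (B) eight candidates, with baseline–change correlation of size 0.3–0.7; (C) ten correlated candidates, with and without carry-over from earlier supplements.

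| Analysis | Quantity | A | B | C |
|---|---|---|---|---|
| Treatment kept in | Type I error, entry 0.05 | 0.075–0.10 | 0.08–0.095 | 0.076–0.090 |
| Treatment kept in | Type I error, entry 0.15 | 0.12–0.14 | 0.10–0.12 | 0.099–0.110 |
| Treatment kept in | Coverage of nominal 90% CI | 0.79–0.86 | not run | 0.82–0.87 |
| Covariates chosen first | Type I error | 0.05–0.06 | not run | 0.049–0.056 |
| Covariates chosen first | Power | 0.65–0.74 | not run | 0.65–0.71 (entry 0.15) |
| Fixed baseline model | Type I error | nominal | 0.052–0.057 | 0.046–0.054 |

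The fixed model's 90% interval covers 0.90 in set-up C. Its power is 0.77–0.85 in set-up A. At 12 per arm, forward selection with treatment kept in still gives a type I error of 0.069–0.080 (entry 0.05) and 0.086–0.095 (entry 0.15).

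**5. Does forward selection pick up baseline?** In set-up B it does so in 20–85% of trials at entry 0.05 and 34–89% at entry 0.15, depending on the correlation. The imbalance rule (p < 0.05) and forward selection (entry 0.15) disagree about including baseline in 36–85% of trials.

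**6. Earlier supplement use.** Let f be the share of ex-users and s the extra fall in their day 0–29 change. Then SD = √(15² + f(1 − f)s²). With first-order decay from Day −15 and assumed half-lives of 14, 28 and 56 days, the fall over day 0–29 is 0.363, 0.353 and 0.250 of the excess at stopping.

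- Excess of 20 points at stopping, f = 0.3, half-life 14 days: s = 20 × 0.363 = 7.26, SD = √(225 + 0.21 × 52.7) = 15.36, power 0.786.
- Same excess, f = 0.1, half-life 56 days: s = 5, SD = √(225 + 0.09 × 25) = 15.07, power 0.801.
- A shift of s = 20 would bring power down to 0.67–0.75 (f = 0.1–0.3). It needs an excess at stopping of 20/0.363 ≈ 55 to 20/0.250 = 80 points.

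**The case against.** **The two sections can be read together**, one naming which variables may be used and the other how they are evaluated. That softens the conflict, but the result is still a data-dependent model. If any numerical difference counted as a difference, baseline would nearly always enter under the first rule, so the 5% figure belongs only to the p < 0.05 reading. The imbalance rule does not inflate type I error either. Both points stand.

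**Entry threshold and order of selection are normal analysis-plan details.** This is true, and the error inflation appears only when treatment is kept in. The other order costs power instead, so settling these details moves the harm without removing it. A plan that fixed one model would still have to override at least one of the two sections.

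**Data Analysis describes no equivalence interval.** The coverage figures therefore matter only if equivalence is judged from an interval. The type I error and power figures do not depend on that.

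**The fix can cost power.** With no baseline–change correlation, it falls below the planned 0.80. This stands and is priced below.

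**A reader might infer that the short washout undermines the trial.** The documents do not support that. Allocation follows the run-in, so earlier use is balanced in expectation. Blood is drawn before and after the run-in, the pre-screening survey checks the criterion, and the outcome is a change. Only an excess at stopping far above the 20-point meaningful difference would cost appreciable power. Admitting willing recent users is a recruitment choice.

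**Conclusion.** The concern holds as a minor fault in how the primary analysis is specified. Two stated rules for one covariate conflict, neither ensures adjustment, and forward selection performs worse than a fixed model on either reading. With entry p between 0.05 and 0.15 and 10 per arm, type I error is about 0.08–0.14 with intervals that are too narrow, or power is about 0.65–0.74. These figures rest on assumed entry thresholds, correlations and numbers of candidates; the direction is the same in all set-ups. The result does not depend on carry-over. The eligibility wording is a side note: it guarantees only about two weeks of washout for some participants, but with a 20-point excess power stays at about 0.79–0.80 against 0.805.

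**What to change.** In Internal and External Validity and in Data Analysis, replace both rules with one pre-specified model for the change in each erythrocyte fatty acid. Its terms are treatment, the day-0 erythrocyte level of that fatty acid, and gender as the stratification factor. Use the pre-washout level and the remaining covariates only in sensitivity analyses. Baseline comparisons between arms may stay as description, without deciding the model.

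This takes about one sentence in each section. All data are already collected and the planned sample size is unchanged. At 10 per arm, power falls by 0.03–0.04 (0.81 to 0.77) if baseline is unrelated to change. It rises by about 0.03 (0.80–0.81 to 0.83–0.84) if the correlation is −0.4, which is an assumption. At 12 per arm without correlation it goes from 0.88 to 0.86. The main gain is a valid error rate and valid coverage. This fix needs no change to the eligibility criteria.

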### *Sample size justification*

- The sample size (10 per group) was calculated based on a one way ANOVA with a meaningful mean difference of 20%, power of 0.80, alpha of 0.05, and a standard deviation of 15% based on literature values of erythrocyte DHA levels . The expected dropout rate is 20%. Therefore, 24 participants will be recruited.

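### Recruiting 24 with 20% dropout leaves about 19, not the required 20 (power about 0.78, not 0.80), and the power is for DHA levels while the primary outcome is change in EPA and DHA

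*Protocol*

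**What the plan says.** **Sample size justification (section III.B).** Ten per group, from a one-way ANOVA with a mean difference of 20%, power 0.80, alpha 0.05 and a "standard deviation of 15% based on literature values of erythrocyte DHA levels". The step to the recruitment figure is: "The expected dropout rate is 20%. Therefore, 24 participants will be recruited".

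**Biological Measures (section III.C.1).** Here the objective is worded in terms of levels: "the primary objective is to determine if erythrocyte DHA and EPA levels differ after consuming algae oil fortified soymilk" compared with capsules.

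**Data Analysis.** The outcome is now a change, in both fatty acids: "primary outcome of change in erythrocyte EPA and DHA concentration will be evaluated using analysis of variance (ANOVA"). For adjustment, "pre-trial and baseline levels of EPA and DHA will be evaluated using a forward selection procedure", alongside BMI, height, weight, sex, age and ethnicity.

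**Internal and External Validity.** A different rule covers age, BMI and initial EPA and DHA: "If differences in these variables are found, they will be used as covariates in data modeling".

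**Study Phase.** The day-0 sample is already planned: "The visits will occur on day 0, 14, and 29. At each visit, blood will be drawn".

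**The concern.** There are three linked points.

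1. **Dropout step.** The number recruited is presented as a consequence of 10 per group and 20% dropout, but 80% of 24 is less than 20. The figure looks like 20 × 1.20, which adds 20% of the target instead of dividing by the fraction retained.
2. **Basis of the power.** The SD is for DHA levels; the primary outcome is change in EPA and DHA. The protocol does not say whether EPA and DHA are two outcomes or one sum. The variance of a change depends on the correlation between day 0 and day 29, and EPA has its own variance. A power computed for DHA levels therefore does not carry over without further inputs.
3. **Baseline value.** The day-0 measurement links level and change, and it can affect precision as much as the dropout step or more. One section adjusts for it only if the arms are found to differ; the other leaves it to forward selection. These are different data-dependent rules for the same model, so the primary model is not fixed in advance.

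At stake is whether the trial has the power it claims for the outcome it will report.

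**Working it through.** **Inputs from the sample size paragraph:** 10 per group, difference 20%, SD 15%, alpha 0.05, power 0.80, dropout 20%, 24 recruited. Sidedness is not stated; two-sided is assumed, which is what the ANOVA F test gives for two groups.

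**Step 1: reproduce the stated power.** Noncentral t with n1 + n2 − 2 degrees of freedom and noncentrality (20/15) × √(n1·n2/(n1 + n2)).

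| Evaluable | Noncentrality | Power |
|---|---|---|
| 10 + 10 | 1.333 × √5 = 2.98 | 0.805 |
| 10 + 9 | 1.333 × √(90/19) = 2.90 | 0.781 |
| 9 + 9 | 1.333 × √4.5 = 2.83 | 0.757 |

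Ten per group reproduces and is the smallest equal group size that reaches 0.80, so there is no slack.

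**Step 2: the dropout step.**
- Remaining from 24: 24 × 0.80 = 19.2.
- Needed to keep 20: 20/0.80 = 25, or 26 in equal arms.
- Dropout that 24 can absorb: 1 − 20/24 = 16.7%.
- Source of the 24: 20 × 1.20 = 24.

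If dropout is independent at 20%, the chance that at least 20 are evaluable is 0.46 from 24 recruits, 0.62 from 25 and 0.75 from 26. If 12 per arm are randomised and all loss comes afterwards, the power averaged over the binomial outcomes is 0.778 (0.813 with 13 per arm). If all loss comes before a balanced randomisation, it is 0.782. Either way it is about 0.78.

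**Step 3: the margin on the effect size.** Power 0.80 requires difference/SD of at least 1.325 at 10 + 10 and 1.366 at 10 + 9. The protocol supplies 20/15 = 1.333 for DHA levels. That passes the first threshold narrowly and misses the second. It gives no ratio for EPA, the sum or change.

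**Step 4: level against change (sensitivity only).** Assumptions not in the document: SD 15% at both day 0 and day 29, the same 20% difference, and a day-0 to day-29 correlation r.
- Change: SD = 15 × √(2(1 − r)).
- Day 0 as a fixed covariate: SD = 15 × √(1 − r²), with N − 3 degrees of freedom and the variance inflated for chance baseline imbalance, then averaged.

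| r | SD of change | Power at 10 + 9, ANOVA on change | Power at 10 + 9, day 0 as fixed covariate |
|---|---|---|---|
| 0.3 | 17.7% | 0.64 | 0.79 |
| 0.5 | 15.0% | 0.78 | 0.86 |
| 0.7 | 11.6% | 0.94 | 0.96 |

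Simulation with 20,000 runs per value of r agreed to within 0.01. At 10 + 9, power 0.80 needs r of about 0.52 for change and about 0.33 with the covariate. If day 0 were wholly uncorrelated with the outcome, the covariate would reduce power from 0.78 to about 0.75.

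**The case against.** The arithmetic error is hard to dispute. The case against concerns weight and scope.

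- **The shortfall is trivial and enrolment does not change.** True, and it sets the grade. It does not make the sentence right: the stated number does not follow from the stated inputs.
- **Inflating for expected dropout never guarantees the target.** This stands. The 0.46 chance of keeping 20 should be read against 0.62 with 25 recruits and 0.75 with 26, not against certainty. Per-arm probabilities carry little weight here because randomisation follows a two-week run-in, and early losses would never enter an arm. The average power stays at about 0.78 under either pattern of loss.
- **The level-versus-change part shows no error of known direction.** Correct. At r = 0.5 the SD of change is again 15%, and the cited source of the SD cannot be seen, so it may have reported something closer to change. What stands is the mismatch in the text: the paragraph says levels of DHA, and the analysis says change in EPA and DHA.
- **Separate or summed analysis of EPA and DHA can be left to an SAP.** Fair as far as it goes. The combined milligram figure in the Background describes a serving and does not define the blood outcome. But the protocol itself fixes both the sizing variable and the primary outcome, and they differ.
- **The covariate rule is a different issue.** It is an analysis point rather than arithmetic. It belongs here because the day-0 value connects the variable used for sizing to the one analysed.
- **The hypothesis is equivalence, while the 0.80 is power to detect a difference.** This is a separate matter that the present correction does not resolve. The restated power should not be read as power to show equivalence.

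**Conclusion.** The concern holds, as a minor point that should be corrected. On the protocol's own inputs, 24 recruits with 20% dropout give about 19 evaluable and power of about 0.78, against a stated requirement of 20 and 0.80. This assumes a two-sided test at 0.05 and a near-equal split.

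The stated power is supported for erythrocyte DHA levels only. For EPA, for the sum or for change it is not shown, and the document does not allow the gap to be computed. Under the assumed correlations of 0.3 to 0.7, power for change at 10 + 9 runs from 0.64 to 0.94, so the mismatch could matter far more than the dropout step, in either direction.

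The two baseline rules conflict as written. Confidence is high on the arithmetic and on the textual conflicts. No claim is made about the true power for the named primary outcome.

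**What to change.** Keep enrolment at 24 and make three text changes.

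1. **Sample size justification:** state either that about 19 evaluable participants are expected, with power of about 0.78, or that 24 recruits tolerate 16.7% dropout. Add that this power is for detecting a difference in erythrocyte DHA levels, unless a difference and SD for EPA (or for EPA plus DHA) are supplied.
2. **Data Analysis:** include the day-0 value of the fatty acid being analysed as a prespecified covariate, and remove it from the forward-selection candidates.
3. **Internal and External Validity:** align the covariate sentence, so that adjustment for initial EPA and DHA no longer depends on whether differences are found.

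The cost is one paragraph and two sentences. No recruits, visits or samples are added, because day-0 blood is already drawn. The stated power becomes slightly less favourable. The covariate uses one degree of freedom, and its worst case is the fall from 0.78 to about 0.75 at 10 + 9 if day 0 carries no information about the outcome.
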